8.8.1.3 Open-Label Extension Phase (26 weeks)

Clinic Visits Visit: Month 7, 9 and 12 (\pm 5 days)

The following assessments will be done:

- Physical examination
- Body weight
- Vital signs including supine blood pressure, respiratory rate, heart rate, and temperature
- 12-lead ECG at Hour 1.5 (\pm 30 min) post dose
- Fasting safety labs chemistry (including CPK, liver enzymes, lipid panel) hematology, and urinalysis labs
- Urine β-hCG (pre-menopausal females)

- Blood Sample for biomarker (Month 12 only)
- Pulmonary function test (Months 9 and 12 only)
- 6MWT (Months 9 and 12 only)
- Dyspnea score (MMRC)
- ATAQ-IPF (Months 9 and 12 only)
- Adverse event review
- Concomitant medication review
- Patient diary review (and collect at Month 12)
- Dispense study drug (Month 9)
- Study drug accountability
- Study drug return (at Month 12)

Telephone Visits: Week 27 (\pm 3 days), Month 10 (\pm 5 days)

Between clinic visits, subjects will be called by a study team member (e.g., study coordinator or nurse) to collect information regarding their health status. The MMRC (Month 10 only) will be administered and adverse events and concomitant medications will be documented.

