- Any significant laboratory abnormality which, in the opinion of the Investigator, may put the subject at risk
- History of malignancy < 5 years prior to signing the informed consent, except for adequately treated basal cell or squamous cell skin cancer or *in situ* cervical cancer.
- History or evidence of drug or alcohol abuse
- History of HIV (human immunodeficiency virus) or other active infection.
- Currently has a clinically significant medical condition including the following: neurological, psychiatric, immunological, metabolic, hepatic, hematological, pulmonary (other than IPF), cardiovascular (including uncontrolled hypertension), gastrointestinal, urological disorder, or central nervous system (CNS) infection that would pose a risk to the subject if they were to participate in the study or that might confound the results of the study.

Note: Active medical conditions that are minor or well-controlled are not exclusionary if, in the judgment of the Investigator, they do not affect risk to the subject or the study results. In cases in which the impact of the condition upon risk to the subject or study results is unclear, the Medical

Monitor should be consulted.

- CYP2C8 and CYP2C9 substrates with narrow therapeutic indices (i.e. paclitaxel, phenytoin and S-warfarin) within 14 days of Screening Visit and throughout the study.
- Macrolide or quinolone class antibiotics within 14 days of Screening Visit and throughout the study.
- Poor peripheral venous access that will limit the ability to draw blood as judged by the Investigator.
- Currently participating, or has participated in, a study with an investigational or marketed compound or device within 3 months prior to signing the informed consent.
- Unwilling or unable to conduct Spirometry (Vital Capacity) test.
- Unable to cooperate with any study procedures, unlikely to adhere to the study procedures and keep appointments, in the opinion of the Investigator, or is planning to relocate during the study.

Investigational Product, Dosage and Mode of Administration: Three MN-001 tablets (750 mg) or matching placebo to be administered orally twice daily or two tablets (500 mg) or matching placebo to be administered three times daily for a total daily dose of 1500 mg.

Duration of Treatment: approximately 12 months/52 weeks

Reference Therapy, Dosage, and Mode of Administration: matching-placebo

Criteria for Evaluation

Efficacy Endpoints:

Efficacy will be assessed by the following:

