- FVC and FVC% predicted up to 26 weeks
- Semiannual decline on disease activity based on forced vital capacity (FVC)
- Annual/semiannual decline on disease activity based on the 6-minute walk test (6MWT)
- Modified Medical Research Council Dyspnea Score (MMRC)
- Quality of life (QOL) measured by A Tool to Assess Quality of Life in Idiopathic Pulmonary Fibrosis (ATAQ-IPF)
- Frequency of worsening IPF
- Time to first worsening IPF

Safety Endpoints:

The proportion of subjects with:

- Treatment-emergent adverse events (TEAEs)
- Treatment-emergent serious adverse events (TESAEs)
- Treatment discontinuations due to treatment-emergent adverse events

Additional Safety Endpoints:

• Laboratory measures (chemistry, hematology, urinalysis), vital signs, and 12 lead-electrocardiograms (ECGs).

Sample Size Justification

No prior data are available on which to base assumptions for sample size/power considerations. The results of this pilot study will be used to design future studies, and the sample size of approximately 15 subjects is deemed to be appropriate for this purpose.

Table 1: Schedule of Events

Phase	Scree	ening		1	Double-Bli	ind Treatn	nent	ont Open-Label Extension Follow -up End of Study			Open-Label Extension				Early Lab Termination ^c retest ^f	
	Day -90 to -8	Day -7 (±5d)	Day 1	Week 1 (±3d)	Month 1 (±5d)	Month 3 (±5d)	Month 4 (±5d)	Month 6 (±5d)	Week 27 (±3d)	Month 7 (±5d)	Month 9 (±5d)	Month 10 (±5d)	Month 12 (±5d)	Month 13 (±5d)		
Visit Type	Clinic	Clinic	Clinic	Tel	Clinic	Clinic	Tel	Clinic	Tel	Clinic	Clinic	Tel	Clinic	Clinic		
Study Visit Number	1	2	3	4	5	6	7	8	9	10	11	12	13	14	ET	LRT
Informed consent	X ^{a b}	X^{b}														
Inclusion/exclusion criteria review		X	X													
Medication history		X														
Physical Examination		X			X	X		X		X	X		X	X	X	
Body height		X														
Body weight		X			X	X		X		X	X		X	X	X	
Vital signs (sitting)		X	X		X	X		X		X	X		X	X	X	
12-lead ECG		X	Xg		X	X		X		X	X		X		X^{d}	
CBC/CMP, CK, UA Fasting lipid panel		X			X	X		X		X	X		X		X^{d}	X
Serum pregnancy test		X														
Urine pregnancy test			X		X	X		X		X	X		X		X^{d}	
Pulmonary function		X				X		X			X		X		X^{d}	
6 minute-walk test		X^h				X^h		X^h			X		X		X^{d}	
ATAQ-IPF		X				X		X			X		X		X^{d}	
MMRC		X			X	X	X	X		X	X	X	X		X^{d}	
Plasma for Biomarker		X						X					X		X^{d}	
Adverse event review			X	X	X	X	X	X	X	X	X	X	X	X	X	X
Concomitant med review			X	X	X	X	X	X	X	X	X	X	X	X	X	X
Study Drug Dispensing			X		X	X		Xe		X	X		X			

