6.4. Follow-up Phase

All subjects who complete the study will return for their final visit at 4 weeks after their last dose for safety assessments and to assess adverse event status and document concomitant medications.

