8.8.1.2. Double-Blind Treatment Phase (26 weeks)

Subjects will enter the clinic in the morning prior to breakfast. Once the pre-dose fasting labs have been completed, subjects will be given breakfast except on Baseline Day 1.

Baseline Clinic Visit: Day 1

The following assessment will be done:

- Inclusion/Exclusion criteria review
- Vital signs including supine blood pressure, respiratory rate, heart rate, and temperature
- Urine β-hCG (in pre-menopausal females)
- Concomitant medication review
- Adverse event review
- Dispense study drug
- Dispense patient diary
- 12-lead ECG at Hour 1.5 (\pm 30 minutes) post dose

Once the pre-dose assessments have been completed, the subject will be administered the first dose of MN-001 (2 or 3 tablets of MN-001 250 mg) or matching placebo with water.

Clinic Visits: Months 1, 3 and 6* (± 5 days)

The following assessments will be done:

- Physical examination
- Body weight
- Vital signs including supine blood pressure, respiratory rate, heart rate, and temperature
- 12-lead ECG at Hour 1.5 (± 30 min) post dose

- Fasting safety labs chemistry (including CPK, liver enzymes, lipid panel) hematology, and urinalysis labs
- Urine β-hCG (pre-menopausal females)
- Blood Sample for biomarker (Month 6 only)
- Pulmonary function test (Months 3 and 6 only)
- 6MWT (Months 3 and 6 only)**
- Dyspnea score (MMRC)
- ATAQ-IPF (Months 3 and 6 only)
- Adverse event review
- Concomitant medication review
- Patient diary review
- Dispense study drug (Months 3 and 6 only)
- Study drug accountability
 - * Month 6 Clinic Visit is the start day (Day 1) of the Open-Label Extension (OLE) phase. All subjects will take MN-001 750 mg bid or 500 mg tid.
 - ** Two tests should be performed for 6MWT

Telephone Visits Week 1 (\pm 3 days) and Month 4 (\pm 5 days)

Between clinic visits, subjects will be called by a study team member (e.g., study coordinator or nurse) to collect information regarding their health status. The MMRC will be administered (only Month 4) and adverse events and concomitant medications will be documented.

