8.8.1.4 Follow-up / Laboratory Re-test Visits/ Early termination visit

Follow up clinic visit: Month 13 (\pm 5 days)

- Physical examination
- Body weight
- Vital signs including supine blood pressure, respiratory rate, heart rate, and temperature
- Adverse event review
- Concomitant medication review

Laboratory Re-test visit

Subjects who have clinically significant abnormal lab finding will return for a laboratory re-test visit and will have the following assessments performed:

- Fasting chemistry, hematology, or urinalysis lab, as indicated
- Adverse event review
- Concomitant medication review

Early Termination visit

Subjects who discontinued study medication will undergo the following assessments:

- Physical examination
- Body weight
- Vital signs including supine blood pressure, respiratory rate, heart rate, and temperature
- Adverse event review
- Concomitant medication review
- Patient diary review and collect
- Study drug accountability
- Study drug return
- 12-lead ECG**
- Fasting safety labs chemistry (including CPK, liver enzymes, lipid panel) hematology, and urinalysis labs**
- Urine β-hCG (pre-menopausal females)**
- Blood Sample for biomarker**
- Pulmonary function test**
- 6MWT**7
- Dyspnea score (MMRC)**
- ATAQ-IPF**
 - ** Assessment need not be performed if prior assessment occurred within 1 month of Early Termination Visit.

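### Table 1 and SAP Appendix A mark study drug dispensing at Months 1, 7 and 12, where the visit text does not; at Month 12 the text has drug returned, so the schedules must be reconciled.

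*Protocol*

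**What the plan says.** **Schedule table.** In Table 1 of the protocol synopsis, the "Study Drug Dispensing" row carries a mark at Day 1 and Months 1, 3, 6, 7, 9 and 12. SAP Appendix A has the same marks. Table 1 has no row for drug return.

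**Visit text.** Section 8.8.1.2 dispenses at Day 1 and then lists "Dispense study drug (Months 3 and 6 only") for the Month 1, 3 and 6 visits. Section 8.8.1.3 covers Months 7, 9 and 12 and lists "Dispense study drug (Month 9") together with "Study drug return (at Month 12").

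**Treatment length and follow-up.** The synopsis gives "Duration of Treatment: approximately 12 months/52 weeks". Section 6.3 makes the open-label extension 26 weeks. Section 6.4 has completers "return for their final visit at 4 weeks after their last dose for safety assessments". The synopsis and section 6 place that visit within 4 weeks of the last dose.

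**The last visit.** Under "Follow up clinic visit: Month 13", section 8.8.1.4 lists physical examination, weight, vital signs, adverse event review and concomitant medication review, and nothing else.

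**The concern.** Sections 6.2 and 6.3 send the reader to Table 1 for the visit schedule and procedures, so the table is an operative instruction. At Month 12 it has drug given out, while section 8.8.1.3 has drug taken back.

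Month 12 is the visit where this matters most. It is the last one with scheduled laboratory tests, ECG, pregnancy test and drug accountability. Any take-home supply given then would have no scheduled check after it. It would also blur the date of last dose, from which the follow-up visit is timed and which SAP 14.1 uses to separate late adverse events. Compliance is computed per visit period from returned counts (protocol 8.4, SAP 12.4), and a Month 12 supply would have no scheduled count.

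Months 1 and 7 are a supply question. Under the visit text, the Day 1 supply must last to Month 3 and the Month 6 supply to Month 9. Table 1 has a further dispensing in each interval.

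**Working it through.** **1. Is the mark real?** Each row was split into its 16 columns. The dispensing row reads Day 1, Months 1, 3, 6, 7, 9 and 12 in both documents, and is blank at Month 13. The ECG and laboratory rows of Table 1 and the accountability row of SAP Appendix A all align on the same columns and are blank at Month 13. The Month 12 mark is therefore not a product of the PDF conversion.

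**2. The two schedules side by side.**

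| Visit | Table 1 and SAP Appendix A | Sections 8.8.1.2 and 8.8.1.3 |
|---|---|---|
| Day 1 | dispense | dispense |
| Month 1 | dispense | none |
| Month 3 | dispense | dispense |
| Month 6 | dispense | dispense |
| Month 7 | dispense | none |
| Month 9 | dispense | dispense |
| Month 12 | dispense | return |
| Month 13 | none | none |

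They differ at Months 1, 7 and 12.

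**3. The plan's own duration.** 26 + 26 = 52 weeks, and 52 × 7 = 364 days. This reproduces the stated duration. With last dosing at Month 12, the Month 13 visit falls one month later: 365.25 / 12 = 30.4 days. With ±5 days at each visit, the range is 30.4 − 10 = 20.4 to 30.4 + 10 = 40.4 days. That is close to the 4 weeks in section 6.4.

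**4. What a Month 12 supply could amount to.** The documents give no quantity. *Assumption:* the supply covers the interval to Month 13. The daily dose is 6 tablets (three twice daily or two three times daily, Table 6).

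- Extra days: 30.4 (20.4 to 40.4)
- Tablets: 6 × 30.4 = about 183 (6 × 20.4 = about 123, to 6 × 40.4 = about 243)
- Share of 364 days: 30.4 / 364 = 8.4% (5.6% to 11.1%)

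On that assumption the Month 13 visit falls about 0 days after the last dose if it is kept at Month 13. If section 6.4 governs instead, the visit moves later and no longer matches the Month 13 column.

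**5. Months 1 and 7.** *Assumption:* each supply lasts to the next dispensing visit. Under the visit text, the Day 1 and Month 6 supplies must each cover 3 × 30.4 = 91.3 days, or 6 × 91.3 = about 548 tablets. Under Table 1 they cover 30.4 days, or about 183 tablets. The quantity to hand out at Day 1 and Month 6 therefore depends on which schedule the site reads.

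**The case against.** The best argument against is that the Month 12 mark may not mean take-home drug. The marked visits are exactly the days on which section 9.4 has subjects take their dose in the clinic, and section 8.8.1.3 puts the Month 12 ECG 1.5 hours after a dose. The diary row is marked at the same visits. The mark could simply denote a dosing visit.

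Footnote e of Table 1 tells against this. It is attached to the Month 6 mark in the same row and places dispensing after all procedures are finished. Under section 8.8.1.2 those procedures include an ECG taken after the dose, so the Month 6 mark cannot be the clinic dose. Nothing in the table gives the Month 12 mark another meaning. If another was intended, the table needs a note.

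Other parts of the case against do stand, and they rule out stronger readings that a reader might infer:

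- *That a further month of dosing is planned for every completer.* No section states a Month 12 quantity or instructs dosing beyond 52 weeks, and SAP Appendix A places Month 13 under follow-up, outside the extension.
- *That off-drug follow-up is lost.* This holds only if Month 13 stays fixed. Section 6.4 has subjects "return for their final visit at 4 weeks after their last dose", so a later last dose would either move the visit or conflict with the Month 13 column.
- *That leftover drug would never be collected.* Section 9.4 asks for unused drug back at each visit, and section 9.5 requires records of tablets dispensed and returned. What is missing at Month 13 is a scheduled accountability or return step.
- *That the 7-day TEAE window would run past last contact.* SAP 14.1 and 15 change the protocol's TEAE definition.
- *That the 30-day contraception period would outrun follow-up because of this mark.* It already exceeds a follow-up visit within 4 weeks (28 days) under the stated 52-week schedule.
- *That earlier exposure of at most 12 weeks makes the mark worse.* The planned 52 weeks already exceeds that figure.

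**Conclusion.** The contradiction is certain and stands in both documents: three visits disagree, and at Month 12 one instruction is the reverse of the other. Dispensing at Month 12 also fails to fit the extension length, the stated treatment duration and the timing of the final visit. It is an internal inconsistency in an operative schedule. No efficacy analysis in the SAP uses the dispensing row.

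The consequence is conditional. It requires a site to follow Table 1 alone and the Month 12 supply to run to Month 13, which the documents do not state. On those assumptions a completer could receive about 30 more days of drug (20 to 40), with no laboratory tests, ECG, pregnancy test or accountability scheduled afterwards, and Month 13 would fall on or near treatment unless the visit were moved. At most, this concerns the approximately 15 subjects planned. Correction is worthwhile because it bears on safety cover at the end of treatment and is easily made.

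**What to change.** Reconcile the dispensing row of Table 1 and SAP Appendix A with protocol sections 8.8.1.2 and 8.8.1.3 for Months 1, 7 and 12. The last dispensing visit, drug return, the stated treatment duration and the follow-up timed from the last dose should then agree wherever they appear. If the Month 12 mark means something other than take-home supply, a footnote should say so. Which dispensing schedule is right is for the sponsor to settle.

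Section 9.5 already has the CRF record dosing start and stop dates and tablets dispensed and returned. A listing of these by subject would show whether any drug was given out at Month 12.

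The cost is one table row in each document, or the matching lines of the visit text, plus a listing from data already collected. Reconciliation within the stated 52 weeks adds no visit and no test.

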8.8.1.4 Follow-up / Laboratory Re-test Visits/ Early termination visit

Follow up clinic visit: Month 13 (\pm 5 days)

- Physical examination
- Body weight
- Vital signs including supine blood pressure, respiratory rate, heart rate, and temperature
- Adverse event review
- Concomitant medication review

Laboratory Re-test visit

Subjects who have clinically significant abnormal lab finding will return for a laboratory re-test visit and will have the following assessments performed:

- Fasting chemistry, hematology, or urinalysis lab, as indicated
- Adverse event review
- Concomitant medication review

Early Termination visit

Subjects who discontinued study medication will undergo the following assessments:

- Physical examination
- Body weight
- Vital signs including supine blood pressure, respiratory rate, heart rate, and temperature
- Adverse event review
- Concomitant medication review
- Patient diary review and collect
- Study drug accountability
- Study drug return
- 12-lead ECG**
- Fasting safety labs chemistry (including CPK, liver enzymes, lipid panel) hematology, and urinalysis labs**
- Urine β-hCG (pre-menopausal females)**
- Blood Sample for biomarker**
- Pulmonary function test**
- 6MWT**7
- Dyspnea score (MMRC)**
- ATAQ-IPF**
 - ** Assessment need not be performed if prior assessment occurred within 1 month of Early Termination Visit.

8.8.2. Procedures/Assessment Details

8.8.2.1. Informed Consent

The Principal Investigator or a qualified designee (e.g., a licensed, qualified medical practitioner such as a physician's assistant or a nurse practitioner) listed on Form FDA 1572 will explain the study to the subject, answer all of the subject's questions, and obtain written informed consent before performing any study-related procedure. Informed Consent should be conducted in accordance with local requirements. Subjects should be able to verbally describe the benefits and risks associated with this study and what other treatment alternatives are available (as described in the consent form). Only subjects who provide informed consent, as assessed and documented by the Investigator, will be enrolled.

8.8.2.2. Medical History

A medical history obtained by the PI or qualified designee as listed on the Form FDA 1572.

8.8.2.3. Prior/Concomitant Medication Review

Site study staff will record all medications used to treat Idiopathic Pulmonary Fibrosis taken within 1 month prior to screening visit in the CRF. Also, the following parameters will be recorded for all concomitant medications: drug name, route of administration, total daily dose, unit, frequency, start/stop dates, indication, and whether the medication was started after last dose of study medication. The concomitant medications will subsequently be coded using the World Health Organization Drug Dictionary (WHO-DD).

8.8.2.4. Physical Examination

The physical exams must be performed by the PI or qualified designee (physician, physician's assistant or nurse practitioner) listed on the Form FDA 1572. Clinically significant changes from the signing of the informed consent form (ICF) should be captured as AEs in the CRF.

A complete physical examination includes the following assessments: general appearance, head, eyes, ears/nose/throat, neck, lymph nodes, skin, lungs, heart, abdomen, and musculoskeletal. If the subject is discontinued for any reason, every attempt should be made to perform a final physical examination.

8.8.2.5. Vital Signs, Height, and Weight

Blood pressure (BP) and heart rate (HR) measurements will be taken in a supine position. Respiratory rate and temperature will also be measured and all measurements will be recorded in the CRF. Clinically significant changes from baseline should be captured as AEs in the CRF.

Weight will be measured in pounds. Height (in inches) will be recorded only at Visit 2 (Screening).

8.8.2.6. Electrocardiogram (12-Lead ECG)

All subjects will have standard resting 12-lead ECGs performed and interpreted. Subjects are to be supine for at least 5 minutes prior to ECG assessments. The time the ECG is performed will be recorded (using a 24-h clock).

The PI or a qualified designee listed on Form Food and Drug Administration (FDA) 1572 must review, initial, and date the report, which must be filed in the subject's study chart. Clinically significant findings at screening must be captured in the medical history. Any clinically significant changes compared post study drug administration must be captured as an adverse event in the CRF.

8.8.2.7. Pulmonary Function Test

8.8.2.7.1. Forced Vital Capacity

Forced vital capacity (FVC) is an index of respiratory function measured by a spirometry and an established measure of pulmonary function in IPF subjects. Forced vital capacity (FVC) is the volume of air that can forcibly be blown out after full inspiration measured in liters. FVC is the most basic maneuver in spirometry tests.

8.8.2.7.2. Diffusing capacity of the lungs for carbon monoxide (DLCO)

A test of the diffusing capacity of the lungs for carbon monoxide (DLCO) is one of the most clinically valuable tests of lung function. DLCO measures the ability of the lungs to transfer gas from inhaled air to the red cells in pulmonary capillaries (Macintyre et al 2005). This is quick, safe, and useful in the evaluation of both restrictive and obstructive disease.

8.8.2.8. 6-Minute Walk Test (6MWT)

The indication for the 6MWT (ATS Guideline 2002) is for measuring the response to medical interventions in patients with moderate to severe heart or lung disease. Prior to the test, the participant should sit in a chair, located near the starting position for at least 10 minutes before assessing pulse and SpO₂ (and Blood Pressure if not taken and recorded within 4 hours prior to test). The following items will be measured:

- Change in 6MWT distance
- Change in 6MWT oxygen saturation area under the curve using the same oxygen dose as the baseline (Visit 2)
- Change in 6MWT minutes walked

The full 6MWT guideline is found in Appendix 2.

